Date: April 1, 2021

Official title of the study: Pneumococcal nasopharyngeal and oropharyngeal carriage in adults older than 50 years of age in outpatient health care facility in Novi Sad

NCT04831788

Institution Name	University of Novi Sad, Medical Faculty	
Investigator Contact Information: - Full address - Phone No. - Fax No. - e-mail address	Name:	[name]
	Title:	Professor, MD, PhD
	Address 1	[name]
	Address 2	[name]
	City, ST, Zip	21101 Novi Sad, Serbia
	Phone/[contact]/ [name]
	E-mail:	[contact]

STUDY PROTOCOL

Objectives and hypothesis

Primary objective:

- To analyze overall serotype distribution of *Streptococcus pneumoniae* nasopharyngeal and oropharyngeal carriage among adults older than 50 years of age in the city of Novi Sad

Secondary objectives:

- To determine serotype on NP and OP carriage with pneumococcal serotypes among adults older than 50 years of age in the city of Novi Sad according to specific clinical indications set for the PPV or PCV

Clinical hypotheses.

- *Streptococcus pneumoniae nasopharyngeal and oropharyngeal carriage among adults older than 50 years of age in the city of Novi Sad is most probably present in less than 10% of the total population.*
- *Streptococcus pneumoniae serotypes covered by PPV or PCV are represented by more than 60% and 50% of the serotypes in overall distribution among tested subjects.*

Study design

Research center(s):

The research will be carried out by the:

1. Institute of Public Health of Vojvodina
 - Centre for Disease Control and Prevention and the Centre for Microbiology
2. Health Care Centre of Novi Sad
 - Department of General Medicine.

Patients

A prospective study will be conducted. We will sample the population based on voluntary participation. The target group of the research will be all adults who will visit their elected physicians in the Health Care Centre of Novi Sad (outpatient care facility). Only adults older than 50 years of age from Novi Sad with 341,624 (2011 Census) inhabitants will be recruited in this research.

All patients older than 50 years of age will be interviewed by physicians at the admission.

Nasopharyngeal and oropharyngeal swabs will be obtained and transported to the Institute of Public Health for the laboratory analyses. This research represents a baseline measurement of NP carriage of pneumococci in adults older than 50 years of age. It will contribute to the strengthening of the surveillance and allow us to compare the situation on possible serotype replacement once after PPV or PCV are introduced into this age group and higher immunization coverage among high risk groups is achieved.

Inclusion criteria

Adults older than 50 years of age visiting the Health Care Centre with or without signs of upper respiratory tract infection during the study period.

Exclusion criteria

Living outside of Novi Sad, use of oral antibiotics in the two weeks prior to taking the swab and presence of a confirmed immunodeficiency (hematological malignancies, inherited immunodeficiency, HIV, post-splenectomy status, cancer chemotherapy).

Ethics approval

The study protocol will be approved by the Ethics Committee of the Medical faculty of Novi Sad.

Sample processing

To confirm the NP and OP carriage, sampling will include NP and OP swabs. Swabs will be collected by the general practitioners in the Health Care Centre of Novi Sad and will transport, within 24h of collection, to the Centre for Microbiology of Institute of Public Health of Vojvodina, Novi Sad. The sterile cotton-tipped wire swabs will be inserted into the anterior nares, gently rubbed on the NP swab wall and immediately placed in transport medium (Copan Venturi Transystem, Brescia, Italy).

Laboratory procedure

Within the laboratory NP swabs will be analyzed by 200 µl of swab-inoculated STGG media will be transferred to 5.0 ml Todd Hewitt broth containing 0,5% yeast extract (THY) and 1 ml of rabbit serum and incubated at 35-37 °C for six hours. Cultured broth will be plated on sheep blood agar and incubated in 5% CO₂ at 35-37 °C. After 18-24 hours of incubation, plates will be examined for the appearance of alpha-haemolytic colonies resembling streptococci. Positive samples will be cultured, and optochin disc and bile solubility test will be performed.

Molecular serotyping

DNA Extraction

To obtain DNA extracts for PCR reactions, an overnight growth of blood agar plate will be suspended in 300 µl of 0.85% NaCl, heated to 70 °C for 15 min, spun for 2 min and supernatant will be removed. Pellet will be suspended in 50 µl TE buffer with an addition of 10 µl mutanolysin and 8 µl of hyaluronidase, kept at 37°C for 30 min (to overnight), heated for 10 min at 100°C and spun for 4 min. No more than 2,5 µl of supernatant will be used as DNA template. Extracts will be stored at -20°C until PCR testing (9).

Identification of *S. pneumoniae*

Identification of *S. pneumoniae* will be achieved by amplifying the *lytA* gene using primers and probes recommended by CDC and Quanta Biosciences PerfeCTa1 qPCR ToughMix1, Low Rox™ (Quanta Biosciences, Beverly, USA) (10). LytA positive samples will be further analyzed for serotype identification.

Serotype identification

Conventional multiplex PCR assays will be performed as a series of multiplex reactions, using CDC recommended schemes and primers for pneumococcal serotype deduction and 2X PCR Buffer - QIAGEN Multiplex PCR Kit (Qiagen, Hilden, Germany). The PCR products will be analyzed on 2% NuSieve agarose gels (Cambrex Bio Science, Inc., Rockland, ME), stained with ethidium bromide. Gel images will be recorded BioDocAnalyze system (Analytik Jena, Jena, Germany).

Real Time PCR will be performed optionally in case of any difficulties with conventional PCR. It will be performed, as a series of 21 monoplex assays encompassing 21 serotypes using CDC recommended schemes based on geographic prevalence of serotypes. The assays are multiplexed in a sequential triplex format (three targets/serotypes in one reaction), each detecting targets on FAM, Rox (or Cy5) and Hex channels. Reactions will be performed on ABI 7500 Instruments (Thermo Fisher Scientific, Waltham, USA), using specific primers and probes and Invitrogen-Platinum Quantitive PCR SuperMix (Thermo Fisher Scientific, Waltham, USA).

Susceptibility testing

Susceptibility of Spn isolates to Optochin, Oxacilin, Norfloxacin, Erytromycin, Clindamycin, Tetracycline and Trimetroprim-sulfometoxazole will be determined by the Diffusion method according to the European Committee on Antimicrobial Susceptibility Testing (EUCAST, www.eucast.org).

This baseline assessment is taking into consideration to present descriptive only current results, but they are not separately taken into account for comparative analysis.

The results of laboratory testing, conducted for each patient, will be forwarded to elected physicians who indicated sampling of patient material.

Study procedure

Adults will be recruited during their health examination at Health Care Centre of Novi Sad by their elected physician.

After providing a verbal and written explanation of the research aim (Appendix 1), informed consent (Appendix 2) will be obtained from subjects before enrolment. Personal and confidential information obtained from participants will be removed, except for demographic information, including date of sampling,

age, gender, data on previous upper respiratory tract infection, number of children (siblings) aged 0–10 years residing in the household of participants with pneumococcal and influenza immunization history (because influenza immunization may prevent pneumococcal superinfections), smoking habits of participants and their household members and the information about home residence (Survey Questionnaire- Appendix 3).

Samples will be provided as one NP swab per study subject. Every participant will be assigned only once. Confirmed case is every laboratory tested participant in which, after testing (PCR or ELISA), a positive result is obtained.

Statistical Analysis and Sample Size Justification

Collection of the data

Characteristics of all respondents acquired by questionnaire from Novi Sad, the test results of laboratory testing of samples of participants and the final characterization of *Spn* serotypes will be entered in specially designed database. Personal information of participants will be removed.

Investigator of the research along with statistician will analyze the collected data.

Sample size justification

In accordance with the sample size calculation for a study estimating a population prevalence (11), between 350 and 500 samples are planned to be collected. If more than 500 will be eligible they will all be included. We presume to detect pneumococci in up to 10% PCR-positive to *Spn*. Total number of adults older than 50 years of age is around 120,000, and therefore we expect to collect the sample up to 0.4% of the total targeted population.

Expected results

After carefully implementation of the research, we expected that *Spn* carriage among adults older than 50 years of age will be present in less than 10% of the total population. In addition, we presume that *Spn* serotypes covered by PPV or PCV will represent more than 60% and 50% of the serotypes in overall distribution among tested subjects.

Statistical Methods

We will examine associations between risk factors and NP and OP carriage of pneumococci in participants aged older than 50 years. The following factors will be examined as possible risk factors in covered population: age, gender, data on previous upper respiratory tract infection, number of children (siblings) aged 0–10 years residing in the household of participants with pneumococcal and influenza immunization history, smoking habits of participants and their household members and the information about home residence. These factors will be analyzed by univariate and multivariate analyses (if appropriate). Also, the prevalence of NP and OP carriage as the proportion of participants whose nasopharyngeal cultures were positive for *Spn* and corresponding 95% confidence intervals will be estimated. All descriptive analyses will be performed using the SPSS Statistics software Version 21.0 (IBM Corp., Armonk, NY, USA).

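### The antibiotic exclusion names only the oral route, so people recently given injected or infused antibiotics stay eligible; the likely effect is a small downward bias in carriage prevalence

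*Combined protocol and SAP*

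**What the plan says.** The Exclusion criteria name three things. Two are residence elsewhere than in the city and a confirmed immune deficiency of one of five listed kinds. The third is "use of oral antibiotics in the two weeks prior to taking the swab". Nothing there refers to injected or infused antibiotics or to a recent hospital stay, and no reason is given for limiting the rule to the oral route.

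The Inclusion criteria are broad, taking adults over 50 "visiting the Health Care Centre with or without signs of upper respiratory tract infection during the study period".

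Detection as described runs through growth. Swab material goes into broth and then onto blood agar (Laboratory procedure). DNA for the PCR steps comes from that growth: "an overnight growth of blood agar plate will be suspended in 300 µl of 0.85% NaCl" (DNA Extraction). Under Statistical Methods, prevalence is "the proportion of participants whose nasopharyngeal cultures were positive for *Spn* and corresponding 95% confidence intervals will be estimated". Study procedure has each participant enter once, with one nasopharyngeal swab.

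The candidate risk factors in Statistical Methods begin with "age, gender, data on previous upper respiratory tract infection, number of children (siblings) aged 0–10 years residing in the household of participants" and go on to immunization history, smoking and residence. Antibiotic use by any route is not listed there, nor among the items retained under Study procedure.

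**The concern.** By excluding recent oral users, the plan treats recent antibiotic exposure as a reason not to trust a swab result. That reasoning does not depend on how the drug was given. Applied literally, the rule turns away a patient who took tablets last week and admits one who had an injection three days ago.

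If such a person carries pneumococci at a level held below what will grow, the swab is negative and the person counts as a non-carrier. PCR does not recover the case, because its template comes from the plate, and no later swab is planned. The error can only lower the prevalence estimate, and a larger sample does not shrink it. The study is also meant as a baseline for later comparison after vaccine introduction, so a clean eligibility definition has some value beyond this survey.

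**Working it through.** **The plan's own figures.** The documents give no rate of non-oral antibiotic use and no suppression rate, so there is no stated figure for this point to reproduce. The related figures are:

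- Planned sample: 350 to 500 (Sample size justification). No target precision is stated, so the range cannot be derived uniquely. It is consistent with n = z²p(1−p)/d² at p = 10% and d = 3 points, which gives 385.
- Sampling fraction: 500/120,000 = 0.417%, in line with the stated figure of up to 0.4%.
- Expected carriage: up to 10%, hence 35 carriers at n = 350 and 50 at n = 500.

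**Sampling error for comparison.** The 95% half-width is 1.96 × √(0.10 × 0.90/n):

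- n = 350: 3.14 points
- n = 500: 2.63 points

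**Bias.** Let f be the share of participants with a non-oral systemic antibiotic in the two weeks, and s the share of carriage in them that is missed. Then observed prevalence = p(1 − f·s). Both f and s are assumptions. With p = 10%:

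| f | s | Observed | Shortfall (points) | Carriers missed, n = 350 | Carriers missed, n = 500 |
|---|---|---|---|---|---|
| 1% | 0.5 | 9.95% | 0.05 | 0.18 | 0.25 |
| 1% | 0.9 | 9.91% | 0.09 | 0.32 | 0.45 |
| 5% | 0.5 | 9.75% | 0.25 | 0.88 | 1.25 |
| 5% | 0.9 | 9.55% | 0.45 | 1.58 | 2.25 |

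The largest shortfall relative to sampling error is 0.45/2.63 = 17% of the half-width at n = 500, and 0.45/3.14 = 14% at n = 350.

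**Wider range.** With f from 0.5% to 10% and s from 0.5 to 1, the shortfall runs from 10 × 0.005 × 0.5 = 0.025 points to 10 × 0.10 × 1 = 1.0 point. The upper end is 1.0/2.63 = 38% of the half-width at n = 500, but it needs one participant in ten to be exposed and every carrier among them to be missed.

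**Does anything else close the gap?** The residence and immunodeficiency exclusions do not catch an otherwise eligible patient treated by injection or infusion. The case definition under Study procedure allows PCR or ELISA. The PCR route depends on growth, and no ELISA step is described in the laboratory sections.

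**The case against.** The strongest reply is that the effect is negligible and rests on invented inputs. On the assumed ranges it is at most about two carriers and a fraction of the sampling error. This stands, and it sets the priority.

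A second reply concerns the target quantity. If treatment has really cleared carriage, a negative swab is a correct point-prevalence result and not a misclassification. The protocol does not state the purpose of the exclusion, so this cannot be ruled out. It does not rescue the wording, though: the same argument would apply to oral users, whom the plan excludes. If the target is people without recent antibiotic exposure, non-oral users belong outside it too.

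A third reply is that the exposure may well be recorded. The list under Study procedure describes what is kept after personal data are removed, not everything asked; physicians interview each patient; and the questionnaire is an appendix not in the text available. A reader might infer that exposed participants could never be identified. The documents do not support that. They show only that antibiotic exposure is not among the listed items.

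**Conclusion.** The gap in the wording is real: the rule admits by one route an exposure that the plan treats as disqualifying by another. The likely consequence is a small downward bias in prevalence, 0.05 to 0.45 points at a true 10%, or a relative loss of 0.5 to 4.5%. This rests on assumed exposure of 1 to 5%, on assumed suppression of 50 to 90%, and on the exposed participants still being carriers.

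Three stronger readings are tempting but not supported:

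- **That the bias helps confirm the hypothesis of carriage below 10%.** The direction is right, but the plan specifies an estimate with a confidence interval and no test or decision rule against 10%. A shift of this size would rarely alter the conclusion.
- **That it weakens the association between respiratory infection and carriage.** This needs non-oral treatment to be concentrated in people with recent infection. The documents give no such figure and, in the text available, no time window for previous infection. The oral exclusion already removes those treated by that route.
- **That it distorts the serotype distribution or the susceptibility pattern.** Serotype distribution is the primary objective, but selective loss of particular strains is inference without a figure. The Susceptibility testing section presents its results as descriptive and not for comparative analysis.

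Minor priority; a cheap improvement.

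**What to change.** Reword the criterion to exclude use of any systemic antibiotic, oral or parenteral, in the stated two weeks before the swab. Retain a yes/no item on antibiotic exposure in that window in the analysis database, so that eligibility can be checked at data review. If some participants were enrolled under the oral-only wording, the same item allows the prevalence estimate to be repeated without those exposed. If oral-only is intended, the protocol should say why.

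The cost is a short wording change, one question in an interview that already takes place, and some additional exclusions. On the assumed exposure of 1 to 5% these number between 350 × 0.01 = 3.5 and 500 × 0.05 = 25 people, who can be replaced from a target group of about 120,000. No stated sample size or analysis changes.

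### The only child-related risk factor is worded for siblings, which cannot fit adults over 50, and it leaves people whose child contact is outside the home in the reference group

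*Combined protocol and SAP*

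**What the plan says.** The Patients section limits enrolment by age and place: "Only adults older than 50 years of age from Novi Sad". Under Study procedure, the data kept for each participant include the "number of children (siblings) aged 0–10 years residing in the household of participants". Statistical Methods repeats the item as a candidate risk factor: "number of children (siblings) aged 0–10 years residing in the household of participants with pneumococcal and influenza immunization history". In both places it is the only variable about children. Neither section mentions grandchildren, childcare, or contact with children who live elsewhere.

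Statistical Methods then commits to an association analysis: "We will examine associations between risk factors and NP and OP carriage of pneumococci in participants aged older than 50 years". Each factor is to be analysed univariately and, where appropriate, in a multivariate model. No coding, reference group or limitation is given for the child item.

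On size, the Sample size justification says that "between 350 and 500 samples are planned to be collected", with carriage presumed to be at most 10%.

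**The concern.** There are two separate problems.

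The first is wording. A participant over 50 and a child of at most 10 are at least 40 years apart, so the gloss *siblings* describes a relation that essentially does not occur here. Taken literally, the item is zero for nearly everyone and cannot be analysed. Taken loosely, the interviewing physician must decide which children count, and recording may differ between physicians.

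The second is the comparison group. Someone who looks after grandchildren every day but does not live with them scores zero, as does someone who never meets a small child. If contact outside the home also raises carriage, carriage in the reference group is higher than it would be without any child contact, and the OR for co-residence moves toward 1. A weak result could then be read as saying that young children matter little for carriage in older adults, which the item cannot show.

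**Working it through.** **What the plan supplies.** It gives no share of participants living with a young child, no share with contact elsewhere, and no OR, so there is no plan figure for this item to reproduce. Its sampling fraction does check: 500/120,000 = 0.42%, against a stated 0.4%. At 10% carriage, 350 to 500 samples give 35 to 50 carriers.

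**Assumptions (none from the documents).** Carriage with no child contact p0 = 0.05. True OR for co-residence 3. Share co-resident c = 0.15. Share with contact only elsewhere e = 0.20, 0.35 or 0.50. OR for contact elsewhere either 3 or 1.5.

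**Step 1: carriage by group.** Baseline odds = 0.05/0.95 = 0.0526.
- Co-resident: odds 3 × 0.0526 = 0.1579, so p1 = 0.1579/1.1579 = 0.136.
- Contact elsewhere: pe = 0.136 if its OR is 3. If its OR is 1.5, the odds are 0.0789 and pe = 0.0789/1.0789 = 0.073.

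**Step 2: reference group under the planned item.** Everyone not co-resident is pooled:

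pu = [e × pe + (1 − c − e) × p0] / (1 − c)

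Observed OR = 0.1579 / [pu/(1 − pu)]

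Example with e = 0.35 and equal ORs: pu = (0.35 × 0.1364 + 0.50 × 0.05)/0.85 = 0.0727/0.85 = 0.0856. The odds are 0.0936, and the observed OR is 0.1579/0.0936 = 1.69.

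| e | pu, outside OR 3 | observed OR | pu, outside OR 1.5 | observed OR |
|---|---|---|---|---|
| 0.20 | 0.070 | 2.09 | 0.055 | 2.69 |
| 0.35 | 0.086 | 1.69 | 0.060 | 2.49 |
| 0.50 | 0.101 | 1.41 | 0.064 | 2.32 |

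With equal ORs, varying c from 0.05 to 0.20 gives observed ORs from 1.4 to 2.2. With e = 0, pu = p0 and there is no dilution.

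**Step 3: consistency with the plan's expected carriage.** Overall carriage = c × p1 + (1 − c) × pu. With equal ORs this is 8.0%, 9.3% and 10.6%; the last is above the plan's expectation of under 10%. With an outside OR of 1.5 it is 6.8%, 7.1% and 7.5%.

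**Step 4: a second set-up.** Fix overall carriage at 10%, c = 0.10, equal ORs, and e = 0.10, 0.20 or 0.40. A true OR of 3 is seen as 2.51, 2.14 or 1.63, and a true OR of 2 as 1.81, 1.65 or 1.40. The direction is the same.

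**Step 5: would one pooled 'any contact' exposure be better?** Not necessarily. With c = 0.15, e = 0.35 and an outside OR of 1.5, pooled exposed carriage = (0.15 × 0.1364 + 0.35 × 0.0732)/0.50 = 0.0921. Its odds are 0.1015, and the pooled OR is 0.1015/0.0526 = 1.93. That is further from 3 than the planned item's 2.49.

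**Step 6: three levels, 'neither' as reference.** Each contrast returns its own OR (3 and 1.5 in Step 5's case), because the reference carriage is p0. The cost is precision. At N = 500 in that case, expected carriers are 75 × 0.1364 = 10.2, 175 × 0.0732 = 12.8 and 250 × 0.05 = 12.5. For co-resident against neither, SE(log OR) = √(1/10.2 + 1/64.8 + 1/12.5 + 1/237.5) = 0.444, a 95% interval of ×/÷ exp(1.96 × 0.444) = 2.39. The planned contrast has 25.3 carriers and 399.7 non-carriers in its reference group: SE = √(1/10.2 + 1/64.8 + 1/25.3 + 1/399.7) = 0.394, or ×/÷ 2.16.

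**The case against.** The strongest reply is that nothing is miscoded. The plan never calls the item child contact. It counts children in the home, and for that purpose a participant with no resident child is correctly zero. This stands. A reader might infer that the planned variable is wrong, or that the association is certain to be diluted. The text supports neither: attenuation occurs only if contact outside the home is present and itself raises carriage, and the documents are silent on both.

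A reader might also blame the dilution on the word *siblings*. It is a separate defect. Read sensibly, the item already counts co-resident grandchildren, and the mixed reference group would remain after the word is deleted.

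The size is open as well. The larger attenuation needs contact elsewhere to act as strongly as living with a child; halving that OR to 1.5 removes most of it. Appendix 3 was not in the text reviewed, and the Study procedure list is introduced as a partial one, so the questionnaire may ask more. Against that, the risk-factor list in Statistical Methods has no such item, so nothing further is planned for analysis.

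Finally, the stakes are modest. The objectives and hypotheses concern carriage and serotypes, the sample size is set for a prevalence, and 35 to 50 carriers leave any risk-factor analysis imprecise. It would be wrong to infer that the main results are at risk.

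**Conclusion.** The point holds as a minor, inexpensive improvement to the risk-factor analysis. The wording defect is plain from the text and needs no assumption. The mixed reference group is also plain; its effect is conditional. Under the assumptions in the working (true OR 3, 5% baseline carriage, 15% co-resident, 20% to 50% in contact elsewhere), the observed co-residence OR is about 2.1 to 1.4 if outside contact has the same OR, and about 2.7 to 2.3 if its OR is 1.5. These figures illustrate the mechanism and do not estimate the bias in this study. The prevalence estimate and the serotype distribution do not use the item and are untouched.

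**What to change.** Make three changes in Study procedure, Statistical Methods and the questionnaire, before recruitment:

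1. Replace the sibling gloss so that the item reads: number of children (any relation, including grandchildren) aged 0–10 living in the household.
2. Add one question: regular close contact, for example at least weekly, with any child aged 0–10 living elsewhere.
3. Pre-specify a three-level factor (co-resident; outside contact only; neither) with 'neither' as reference, in place of the bare count and in preference to a single pooled exposure.

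The cost is one extra question, some recall error on it, and one more model term when at most about 35 to 50 carriers are expected. The smaller reference group also widens the co-residence interval, as Step 6 shows. Each participant is enrolled once and identifying details are removed, so the information would be hard to recover later.

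If the question is not added, correct the wording anyway, label the factor as co-residence with a young child, and state that it does not measure child contact in general.

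### Carriage labelled nasopharyngeal and oropharyngeal is calculated from nasopharyngeal cultures alone, and the protocol contradicts itself on whether an oropharyngeal swab is taken

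*Combined protocol and SAP*

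**What the plan says.** **Two sites.** The title, both objectives and the first clinical hypothesis concern nasopharyngeal (NP) and oropharyngeal (OP) carriage. The Patients section says "Nasopharyngeal and oropharyngeal swabs will be obtained and transported to the Institute of Public Health for the laboratory analyses". Sample processing repeats it: "To confirm the NP and OP carriage, sampling will include NP and OP swabs".

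**One site.** Study procedure says "Samples will be provided as one NP swab per study subject". The only collection step described is nasal: "The sterile cotton-tipped wire swabs will be inserted into the anterior nares". The laboratory text opens "Within the laboratory NP swabs will be analyzed by" and gives no step for an OP swab. The Patients section also describes the study as a baseline for NP carriage.

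**Analysis.** Statistical Methods sets "the prevalence of NP and OP carriage as the proportion of participants whose nasopharyngeal cultures were positive for" *Spn*, with 95% confidence intervals, and plans risk-factor analyses of NP and OP carriage.

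**Case definition.** Study procedure says "Confirmed case is every laboratory tested participant in which, after testing (PCR or ELISA), a positive result is obtained". It names no site. The same section adds "Every participant will be assigned only once".

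**The concern.** There are three linked faults.

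1. The two sampling instructions cannot both be carried out. A clinic following one section and a laboratory following another would produce different data.
2. The prevalence is labelled for two sites, but only NP cultures can make a participant positive. Taking and testing every OP swab would not change this: an OP-only carrier would still be counted as negative.
3. If OP swabs are tested, that same participant is a confirmed case under Study procedure and a non-carrier under Statistical Methods. The plan does not say which definition is the risk-factor outcome. It also does not say how serotypes are counted when the two sites differ, although serotype distribution is the primary objective.

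In a descriptive study the estimate is the result. This one is meant as a baseline against which the position after vaccine introduction will be compared, so the site it refers to has to be known.

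**Working it through.** **The plan's own figures.** Sample size justification gives 350 to 500 samples, carriage of up to 10%, and about 120,000 adults in the target group. 500/120,000 = 0.417%, which agrees with the stated 0.4% and shows that a sample is being counted as one person. The precision behind 350–500 is not stated, so that range cannot be strictly reproduced. This does not affect the present point.

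**Formula.** Let P be the either-site prevalence and s the share of carriers positive only in the oropharynx. The rule in Statistical Methods then estimates P × (1 − s). The documents do not give s, and it may be zero. I assume P = 10% and let s run from 0 to 50%.

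**Results.** Expected NP-positive count = n × P × (1 − s). The plan names no interval method; these are Wilson 95% intervals evaluated at the expected count x, with p = x/n and z = 1.96:

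[p + z²/2n ± z√(p(1 − p)/n + z²/4n²)] / (1 + z²/n)

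| s | Expected estimate | n = 500: count (95% CI) | n = 350: count (95% CI) |
|---|---|---|---|
| 0% | 10.0% | 50 (7.7–12.9%) | 35 (7.3–13.6%) |
| 10% | 9.0% | 45 (6.8–11.8%) | 31.5 (6.4–12.5%) |
| 20% | 8.0% | 40 (5.9–10.7%) | 28 (5.6–11.3%) |
| 30% | 7.0% | 35 (5.1–9.6%) | 24.5 (4.8–10.2%) |
| 40% | 6.0% | 30 (4.2–8.4%) | 21 (4.0–9.0%) |
| 50% | 5.0% | 25 (3.4–7.3%) | 17.5 (3.2–7.8%) |

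At the expected count, the interval first excludes the assumed true 10% at s = 30% for n = 500 and at s = 40% for n = 350, on this grid.

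**Coverage.** An interval at the expected count can include 10% while the method covers poorly. Exact coverage is the sum of binomial probabilities, with success probability P(1 − s), over all counts whose interval contains 10%. At s = 20% a nominal 95% Wilson interval covers the either-site prevalence about 71% of the time at n = 500 and 81% at n = 350. For the Wald interval the figures are 59% and 68%.

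**Effect on the 10% expectation.** If the either-site prevalence were 12% and s = 20% (both assumed), the expected estimate would be 12% × 0.80 = 9.6%, on the other side of the 10% mark.

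**The case against.** The strongest reply is that this is really an NP study with over-broad wording. The stated baseline purpose, the nasal collection step, the laboratory text, the single-swab sentence and the prevalence definition all point that way. On that reading no number is biased and only the label is wrong. This is a fair reading, and the second option under the fix serves it. It does not remove the contradiction, because the protocol plans OP swabs in two places and states OP carriage in its title, objectives and hypothesis.

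Second, the plan never says that NP and OP carriage means positive at either site. If it meant positive at both, an NP-only numerator would overstate it. This stands: the direction given here holds for either-site prevalence only. Under either reading the label and the numerator disagree.

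Third, the values of s are illustrative, and the two case definitions also differ in assay (culture in one, PCR or ELISA in the other). A comparison such as 50 confirmed cases against 40 culture positives at s = 20% therefore isolates the site effect only if OP swabs are tested and the assays agree. Both limits stand.

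Finally, the study is descriptive, and the 10% figure is an expectation with no decision rule attached; Expected results states it without naming a site. The consequence is a mislabelled estimate, not a wrong test result.

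**Conclusion.** The concern holds. The sampling sections contradict each other, and the prevalence rule reports an NP figure under a two-site label. That much follows from the text and needs no assumption. For either-site carriage the estimate is too low by the factor (1 − s). The direction is certain for any s above zero, but the size is not known from the documents: with P = 10% the shortfall runs from nothing at s = 0 to 5 percentage points at s = 50%. The effect on serotype distribution, the primary objective, cannot be quantified from the documents.

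This must be settled before sampling starts. Each participant enters once, and no later visit is planned at which a missing OP swab could be taken.

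**What to change.** Decide which sites are swabbed, then make every section agree.

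**Option A: OP swabs are taken, as Patients and Sample processing plan.**
- Change Study procedure to one NP and one OP swab per participant, and write the OP collection and laboratory steps.
- Replace the prevalence sentence in Statistical Methods with: *Carriage will be reported as three proportions of swabbed participants, each with a 95% CI: NP-positive, OP-positive, and positive at either site.* The both-sites proportion then follows as NP + OP − either.
- State which proportion addresses the 10% expectation and which is the risk-factor outcome. Align the confirmed-case definition with it, including the assay that defines a positive.
- State how serotypes are counted when sites differ. For example, the same serotype at both sites of one participant counts once, and two different serotypes count once each.

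Cost: protocol and analysis wording, a written OP workflow, and more laboratory and analysis work. Processing the sites separately raises specimens to 2 × 350 = 700 up to 2 × 500 = 1,000.

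**Option B: only NP swabs are taken.** Remove oropharyngeal carriage from the title, objectives, hypothesis, sampling text and analysis, and draw conclusions on NP carriage only. Cost: wording, and a narrower claim with no oropharyngeal conclusion.
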